3.3. TIMING OF ANALYSIS

A final analysis will be conducted once the last subject completes or discontinues the study, and the resulting clinical database has been cleaned, quality checked, the pre-analysis meeting has occurred, and the final database lock has occurred.

4. ANALYSIS POPULATIONS

The populations for analysis will include the full set, safety (SAF) set, the PK set, and the PK Completer set.

4.1. FULL SET

The full set is the population of all subjects who sign an informed consent form.

4.2. SAFETY SET (SAF)

The SAF set is the population of all subjects who receive at least one dose of roluperidone. Subjects in this population will be analyzed according to the treatment(s) they receive. All safety analyses will be based on this population and treatment assignment.

4.3. PK SET

The PK set will consist of all subjects who completed all the PK assessments of at least 1 study phase, up to and including the 48-hour PK blood sample collection, provided they have no major protocol violations that could affect the pharmacokinetics of roluperidone. The PK evaluations will be based on the PK set.

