6.2. Collection of Blood

The maximum amount of blood drawn per subject in this study will not exceed 500 mL for subjects who complete the study. Repeat or unscheduled samples may be taken for safety reasons.

Table 1: Volume of Blood to be Collected from Each Subject

Type of Sample	Volume per Sample (mL)	No. of Samples per Subject	Total Volume of Blood ^a (mL)
Safety (including screening and post-treatment			
assessments)			
- Hematology	4	5	20
- Clinical chemistry ^b	8.5	5	42.5
- Genotyping	4	1	4
Pharmacokinetic samples (roluperidone / BFB-520)	2.5	70	175
Pharmacokinetic samples (olanzapine)	3	35	105
Loss by use of indwelling intravenous cannula	2	1	2
-		Total:	348.5

^a Calculated as number of samples multiplied by amount of blood per sample.

If blood samples are collected via an indwelling cannula, an appropriate amount (ie, 1 mL) of fluid slightly more than the dead space volume of the lock will be removed from the cannula and discarded before each blood sample is taken. After blood sample collection, the cannula will be flushed with 0.9% pharmaceutical grade for injection sodium chloride, or sodium heparin of 100 U/mL (where applicable) and charged with a volume equal to the dead space volume of the lock.

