7. SUBJECT COMPLETION/WITHDRAWAL

7.1. Completion

A subject will be considered to have completed the study if he or she completed all required assessments at Day 19. Subjects who prematurely discontinue for any reason before completion of Day 19 will not be considered to have completed the study.

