3.2.4. Presentations by Time Point

Subjects are institutionalized from washout phase to Day 19 (+2 days after the last dose on Day 17). See Section 1.2 for specifics regarding when assessments are measured within a phase. The timeline of assessment measurements is repeated for each treatment phase. Assessments after screening and occurring on Day -1 after a washout period will be attributed to the following treatment phase.

Nominal Time Points as obtained from the eCRF or laboratory will be utilized for summary displays. Unscheduled visits will not be windowed and be excluded from summary tables and figures but will be listed.

If assessments are collected multiple times within a given nominal time point, the result closest to the scheduled time will be used for summary presentations. If two measurements have the same distance to the expected time, the earlier value will be used. If a scheduled assessment and an early termination assessment are collected within a given time point window, the value from the scheduled assessment will be chosen over the value from the early termination assessment.

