4.4. PK COMPLETER SET

The PK Completer set will consist of all subjects who completed all the PK assessments, up to and including the 48-hour PK blood sample collection, provided they have no major protocol violations that could affect the pharmacokinetics of roluperidone. Select PK evaluations (C_{max} , AUC_{24} , AUC_{last} , and AUC_{∞}) will be performed for the PK Completer set.

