5.2. PHARMACOKINETIC ANALYSES

The secondary objective of the statistical analysis will be to evaluate the effect of the coadministration of roluperidone and olanzapine on the pharmacokinetics (PK) of roluperidone in subjects with moderate to severe negative symptoms of schizophrenia. The PK parameters of interest will be the natural log-transformed estimated AUCs and C_{max} . Only the data from subjects who completed all the PK assessments, up to and including the 48-hour PK blood sample collections (PK Completer set), will be included in the statistical analysis, but all available data will be analyzed as well (PK set).

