5.2.1. Pharmacokinetic Sampling

During Treatment Phase 1, all subjects will have plasma PK samples will be drawn for roluperidone and its metabolite BFB-520 at 0 (pre-dose), 1, 2, 3, 4, 5, 6, 8, 10, 12, 14, 16, 18, and 24 hours post-dose on Days 1 and 7, at 6 hours post dose on Day 2, and at pre-dose and 6 hours post-dose on Days 3-6. During Treatment Phase 2, PK samples for roluperidone and olanzapine will be obtained at 6 hours post-dose on Day 8, time 0 (pre-dose) and 6 hours post-dose on Days 9-16, and starting on Day 17 at time 0 (pre-dose), 1, 2, 3, 4, 5, 6, 8, 10, 12, 14, 16, 18, 24, 28, 32, 36, and 48 hours post-dose.

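### SAP 4.3 ties PK-set entry to a 48-hour sample that Phase 1 does not have, and SAP 4.4 and 5.2 do not say whether one missed draw removes a subject from the PK analysis

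*SAP*

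**What the plan says.** - **PK set (SAP 4.3).** It takes in subjects who "completed all the PK assessments of at least 1 study phase, up to and including the 48-hour PK blood sample collection", if they have no major violation that could affect roluperidone PK. The section adds that PK evaluations rest on this set.
- **PK Completer set (SAP 4.4).** It consists of "all subjects who completed all the PK assessments, up to and including the 48-hour PK blood sample collection", with the same proviso. Selected parameters are evaluated in it.
- **Use of the sets (SAP 5.2).** Only Completer data feed the main PK comparison, with the PK set alongside: "PK Completer set), will be included in the statistical analysis, but all available data will be analyzed as well (PK set". SAP 5.2.4 names no set for the mixed model. SAP section 9 lists PK-parameter tables for both sets.
- **Sampling (SAP 5.2.1).** Full Phase 1 profiles end with "18, and 24 hours post-dose on Days 1 and 7". The Day 17 profile runs on to "18, 24, 28, 32, 36, and 48 hours post-dose". The other dosing days have one or two draws each.
- **Timeline (SAP 3.2.4).** "The timeline of assessment measurements is repeated for each treatment phase".
- **Protocol.** Section 8.2 defines the PK population by judgement: no major drug-intake deviation, and primary PK data good enough to interpret. Section 7.1 defines study completion: "A subject will be considered to have completed the study if he or she completed all required assessments at Day 19".

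No tolerance for a missed PK sample appears in SAP 3.2.3, 4.3, 4.4, 5.2 or 6. SAP 6 says only that a missing PK assessment may be identified as a protocol deviation.

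**The concern.** Two rules decide who enters the PK analysis, and neither fits the sampling schedule.

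The first is the 48-hour clause in SAP 4.3. Allowing one phase to suffice suggests that Phase 1 alone was meant to qualify a subject, yet Phase 1 has no 48-hour post-dose sample. The one-phase allowance therefore has no effect. A subject who supplied complete Day 1 and Day 7 profiles and then left is outside the set used for the single-dose and monotherapy steady-state tables.

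The second is the all-assessments rule in SAP 4.4 and 5.2. Read plainly, it makes entry depend on draws that the parameters do not use. Missing the 6-hour sample on Day 4, for example, would remove a subject whose Day 7 and Day 17 profiles are both intact.

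At stake is the number of subjects behind the 90% confidence interval for the roluperidone ratio with and without olanzapine. SAP 3.1 bases its precision on 12 subjects who complete dosing, not on 12 who have every sample. If the rule stays open, it will be settled after concentrations are known, in an open-label study.

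**Working it through.** **1. Count the roluperidone draws (SAP 5.2.1).**

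| Days | Draws | Type |
|---|---|---|
| 1 | 14 (0 to 24 h) | profile |
| 2 | 1 | sparse |
| 3-6 | 4 × 2 = 8 | sparse |
| 7 | 14 (0 to 24 h) | profile |
| **Phase 1** | **37** | |
| 8 | 1 | sparse |
| 9-16 | 8 × 2 = 16 | sparse |
| 17 | 18 (0 to 48 h) | profile |
| **Phase 2** | **35** | |
| **Total** | **72** | 46 profile, 26 sparse |

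In protocol 6.2, Table 1, the row "Pharmacokinetic samples (roluperidone / BFB-520" gives 70, two fewer. The olanzapine row gives 35, which matches Phase 2.

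**2. What the draws feed.** SAP Table 1 lists Cmax, Tmax, AUC0-24, AUC-infinity and half-life. The Day 17/Day 7 ratios of Cmax and AUC0-24 need 14 + 14 = 28 draws. AUC-infinity needs 14 + 18 = 32. Adding Day 1 to those 32 gives 46. The other 72 − 46 = 26 go into concentration summaries but into none of these parameters.

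**3. Who is excluded, by reading.**

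| Reading | PK set | Completer set |
|---|---|---|
| Every draw, 48-hour clause literal | all 35 Phase 2 draws | all 72 |
| Every draw, last sample scheduled for the phase | all 37 or all 35 | all 72 |
| Stayed through the end of sampling | isolated miss irrelevant | isolated miss irrelevant |

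On the first reading, one missed Phase 2 draw puts a subject in neither set. On the second, one miss in each phase does so. On the third, isolated misses exclude nobody.

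**4. The plan's precision figure.** SAP 3.1 states maximum imprecision of 20.5% or 30.8% for a within-subject SD of 0.25 or 0.40. With n = 12,

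x = t(0.95, n−1) × SD × √(2/n) × √(χ²(0.90, n−1)/(n−1)), imprecision = 1 − exp(−x),

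gives 20.52% and 30.75%, which agrees. The 90% assurance term (the χ² factor) is inferred, since the SAP does not state its formula. At n = 10 the same formula gives 23.0% and 34.2%.

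**5. Illustration of loss.** The documents give no miss rate. Assume independent misses at rate m per draw, q = 1 − m, and 12 subjects who finish dosing and sampling:

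| Quantity (of 12) | m = 0.1% | 0.25% | 0.5% |
|---|---|---|---|
| Completers, 12q⁷² | 11.2 | 10.0 | 8.4 |
| All 28 ratio draws present, not a Completer, 12(q²⁸ − q⁷²) | 0.5 | 1.2 | 2.1 |
| Excluded solely for sparse draws, 12q⁴⁶(1 − q²⁶) | 0.3 | 0.7 | 1.2 |
| PK set, literal, 12q³⁵ | 11.6 | 11.0 | 10.1 |
| PK set, last scheduled sample, 12(q³⁷ + q³⁵ − q⁷²) | 12.0 | 11.9 | 11.7 |
| All 28 present, in neither set, literal, 12q²⁸(1 − q²¹) | 0.2 | 0.6 | 1.0 |
| Same, last scheduled sample, 12q²⁸(1 − q²³)(1 − q²¹) | 0.01 | 0.03 | 0.11 |

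The exponents 23 and 21 are the draws in each phase outside the 28: 37 − 14 and 35 − 14. If misses cluster within subjects (beta-binomial, assumed intraclass correlation 0.05), expected Completers rise to 11.6, 11.1 and 10.3. On the stay-through reading every loss in the table is zero.

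**The case against.** **Completing may mean staying.** Protocol 7.1 and 8.2 describe completion in terms of reaching Day 19 or finishing the treatment period, and Day 19 is the day of the 48-hour sample. On that reading the Completer losses vanish. This stands as a possibility. Those sections define study completion, though, and SAP 4.4 speaks of all the PK assessments, so they do not settle it.

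**The PK set covers the gap.** SAP 5.2 plans it in the same sentence, SAP 4.3 makes it the basis for PK evaluations, and tables are listed for both sets. Most of this stands: under the last-scheduled-sample reading almost nobody with a computable ratio is lost from both sets. But on the plain reading the PK set also demands every draw of a phase, so it is not all available data.

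**Misses should be rare.** Subjects are inpatients, dosing is observed and indwelling catheters are allowed. Up to about 18 are enrolled to secure 12. If all 18 finished, 18q⁷² would still be 12.5 at m = 0.5%. This stands, and it keeps the severity low.

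**The sparse draws have a use.** Repeated pre-dose samples can support the claim of steady state, and SAP 2 leaves the parameter list open. This also stands. The point is only that missing one does not prevent the listed ratios from being calculated.

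**The SAP may be making protocol 8.2 operational.** That is fair, because 8.2 gives no criteria. An all-draws rule would still be much stricter than a judgement of adequacy, and SAP 7 does not mention the difference.

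**Conclusion.** The set definitions need correcting, at low severity. The 48-hour clause in SAP 4.3 does not fit the Phase 1 schedule under any count. SAP 4.4 and 5.2 either exclude subjects for draws that the ratio does not need or mean something they do not say.

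A reader might go further in three ways that the documents do not support:

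- **That the interaction analysis will fall below 12 subjects.** This is possible but not shown. It depends on an assumed miss rate, on the every-draw reading, and on how many of about 18 finish.
- **That one missed draw necessarily removes a subject from all PK analysis.** This holds only on the every-draw reading with the 48-hour clause taken literally, and then only for a Phase 2 draw.
- **That shutting out Phase 1-only subjects costs the ratio estimate its pairs.** Those subjects have no Day 17 profile, so no within-subject ratio is lost. What is lost is their contribution to the Day 1 and Day 7 summaries. The plan allows for 18 − 12 = 6 who do not finish, so at most about that many are affected, and fewer if some leave before the end of Phase 1.

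PK is a secondary objective, and the safety analyses are unaffected.

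**What to change.** SAP wording only:

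- **4.3.** Replace the 48-hour clause with completion through the last PK sample scheduled for that phase. Also admit any subject with at least one evaluable profile (Day 1, 7 or 17).
- **4.4 and 5.2.** For roluperidone and BFB-520, define Completers by evaluable Cmax and AUC0-24 on both Day 7 and Day 17. For olanzapine, which has no Day 7 profile, require an evaluable Day 17 profile. Judge AUC-infinity profile by profile under the existing Table 1 rule, so that failing it drops only that parameter.
- **Evaluability.** The sponsor sets the limits on missing samples within a profile before any concentration is reviewed.
- **Missed sparse samples.** State that an isolated missed sample outside a profile is listed as a deviation and does not exclude the subject.
- **Optional.** Keep the all-draws set as a sensitivity analysis.

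Two clerical items can be settled at the same time: the SAP 3.2.4 sentence that the timeline repeats in each phase, and 70 versus 72 draws in protocol Table 1. If the set definition still differs from protocol 8.2, say so in SAP 7.

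The cost is slightly more definition and analysis work. Apart from the count in protocol Table 1, the protocol stays as it is, and sampling and conduct do not change.

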4.4. PK COMPLETER SET

The PK Completer set will consist of all subjects who completed all the PK assessments, up to and including the 48-hour PK blood sample collection, provided they have no major protocol violations that could affect the pharmacokinetics of roluperidone. Select PK evaluations (C_{max} , AUC_{24} , AUC_{last} , and AUC_{∞}) will be performed for the PK Completer set.

5. STATISTICAL METHODS

Descriptive statistical methods will be used to summarize the data from this study. Unless stated otherwise, the term "descriptive statistics" refers to number of subjects (n), mean, median, standard deviation (SD), minimum and maximum for continuous data and frequencies and percentages for categorical data, and coefficient of variation (%CV) for PK analysis. All data collected during the study will be included in data listings. Unless otherwise noted, the data will be sorted first by treatment, subject number, and then by date within each subject number. For all other tables presenting data collected on-treatment, summaries will be presented by treatment group.

The term 'treatment group' refers to the administration of roluperidone alone or concomitantly with olanzapine to yield 2 groups.

The statistical analyses will be conducted with the SAS® System version 9.4 or higher. All analyses will be subject to formal verification procedures. Specifically, results will be verified utilizing independent programming prior to issuance of the draft statistical report. All documents will be verified by the lead statistician to ensure accuracy and consistency of analyses.

Final Version

5.1. SUBJECT DISPOSITION, DEMOGRAPHIC AND BASELINE CHARACTERISTICS

Subject disposition will be presented for all subjects and the following will be presented: the number of subjects who meet all eligibility criteria, the number of subjects included in the Full, SAF and PK sets (PK set, and PK Completer set), the number of subjects who completed the study and discontinued from the study, and the reasons for early discontinuation at any point.

Demographic data and Baseline characteristics will be summarized using descriptive statistics for the SAF set. The following variables will be included in the tables:

- Age (years)
- Sex (male/female)
- Ethnicity (Hispanic or Latino/not Hispanic or Latino/ Not Reported)
- Race (American Indian or Alaska Native/Asian/Black or African American/ Native Hawaiian or Other Pacific Islander/White/Not Reported/Other)
- Height (cm)
- Weight (kg)
- Body Mass Index (kg/m2)
- Childbearing potential

This information will be reviewed for Baseline differences, but no statistical testing will be performed.

5.2. PHARMACOKINETIC ANALYSES

The secondary objective of the statistical analysis will be to evaluate the effect of the coadministration of roluperidone and olanzapine on the pharmacokinetics (PK) of roluperidone in subjects with moderate to severe negative symptoms of schizophrenia. The PK parameters of interest will be the natural log-transformed estimated AUCs and C_{max} . Only the data from subjects who completed all the PK assessments, up to and including the 48-hour PK blood sample collections (PK Completer set), will be included in the statistical analysis, but all available data will be analyzed as well (PK set).

5.2.1. Pharmacokinetic Sampling

During Treatment Phase 1, all subjects will have plasma PK samples will be drawn for roluperidone and its metabolite BFB-520 at 0 (pre-dose), 1, 2, 3, 4, 5, 6, 8, 10, 12, 14, 16, 18, and 24 hours post-dose on Days 1 and 7, at 6 hours post dose on Day 2, and at pre-dose and 6 hours post-dose on Days 3-6. During Treatment Phase 2, PK samples for roluperidone and olanzapine will be obtained at 6 hours post-dose on Day 8, time 0 (pre-dose) and 6 hours post-dose on Days 9-16, and starting on Day 17 at time 0 (pre-dose), 1, 2, 3, 4, 5, 6, 8, 10, 12, 14, 16, 18, 24, 28, 32, 36, and 48 hours post-dose.

5.2.2. Assay Results Below the Lower Limit of Quantification

For purposes of calculation, plasma concentration values below the limit of quantification (BLQ) will be treated as zero for the determination of summary and order statistics. For purposes of data presentation, individual values that are BLQ will be presented as "BLQ" in the concentration data

Final Version

listing. If the minimum, median, or maximum concentration is BLQ, it will be presented as BLQ in the table. If the mean concentration is BLQ, it will be presented as BLQ and SD and % coefficient of variation (CV) will be presented as "NA" (not applicable). If 1/3 or more of subjects have values of BLQ at any time point, descriptive statistics will not be calculated at that time point. The Geometric mean will not be calculated at the pre-dose time point. For post-dose values, concentration values equal to one-half the lower level of quantification (i.e., 0.125 ng/mL) will be used for BLQ values for calculation of the geometric mean.

5.2.3. **Pharmacokinetic Methods**

Pharmacokinetic parameters to be estimated from plasma concentration-time data are listed in Table 1.

Table 1. Pharmacokinetic Parameters

Pharmacokinetic Parameter	Definition
C_{max}	Observed maximum plasma concentration (ng/mL)
T_{max}	Time to reach the observed maximum plasma concentration (h)
AUC ₀₋₂₄	Area under the plasma concentration-time curve from time 0 to Concentration $C_{24}(h.ng/mL)$ at the 24-hour time point
AUC_∞	Area under the plasma concentration-time curve from time 0 to infinite time, calculated according to the following equation $AUC = AUC_{last} + C_{last} / \lambda_z \ (h.ng/mL) \), \ where \ Clast \ is the last measurable plasma concentration and \lambda_z is the terminal elimination rate constant$
	AUC $_{\infty}$ will be reported if $t_{1/2,\lambda}$ is calculable and if C_{last} / λ_z represented 30% or less of the AUC value. AUC values where C_{last} / λ_z is less than 30% but greater than or equal to 20% of the AUC value will be flagged in the report.
t _{1/2}	Elimination half-life

5.2.4. Statistical Analyses of Pharmacokinetic Data

Plasma concentration data for roluperidone, BFB-520 and olanzapine will be summarized by treatment group. Nominal time point will be used for presentation of tables and figures. Summaries will include mean, SD, %CV, minimum and maximum.

All estimated PK parameters for roluperidone, BFB-520 and olanzapine will be summarized by treatment group, with summaries including arithmetic mean, median, geometric mean, minimum, maximum, SD, and %CV (arithmetic and geometric) for each treatment. For the calculation of geometric mean, observed values of 0 (BLQ) will be included as 0.0001 before the natural log transformation.

Descriptive summaries of T_{max}, C_{max}, AUC₀₋₂₄, and AUC_∞ will also be summarized within each treatment group.

Final Version

Treatment ratios (roluperidone + olanzapine versus roluperidone alone) for C_{max} , AUC_{0-24} , and AUC_{∞} at steady state will be summarized using the same descriptive statistics as above. LS means ($\pm 90\%$ confidence interval [CI]) for log transformed C_{max} , AUC_{0-24} , and AUC_{∞} will be evaluated by a linear mixed effects model with a fixed term for treatment and a random term for subject, fit by estimated generalized least squares with restricted maximum likelihood estimates of random effects. If deemed relevant to test for a treatment difference in T_{max} , a Wilcoxon signed rank test will be used.

Results for roluperidone, BFB-520, olanzapine will also be presented graphically. Figures will include plasma concentration-time profiles for the mean \pm standard error of mean (SEM), which will be presented by treatment group. Additionally, plasma concentration-time profiles for each subject by treatment group will be presented. All figures will be produced on both the natural log-linear and linear-linear scales.

The plasma pharmacokinetic parameters of olanzapine from Day 17 will be compared with its pharmacokinetic profiles available in published literature.

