8.4. Pharmacokinetic Analyses

The plasma pharmacokinetic parameters after roluperidone single dose, at steady state, and when administered concomitantly with olanzapine (C_{max}, T_{max}, AUC₀₋₂₄, and AUC_∞) of roluperidone and its metabolite BFB-520 will be determined from plasma concentration data using non-compartmental methods. Pharmacokinetic parameters will be summarized by arithmetic mean, SD, geometric mean, coefficient of variation (CV%, both arithmetic and

geometric), median, minimum and maximum.

Plasma concentration data will be summarized by treatment group (roluperidone alone, roluperidone + olanzapine). A nominal time point will be used for the presentation of tables and figures.

Treatment ratios (roluperidone + olanzapine versus roluperidone alone) for C_{max} , AUC_{0-24} , and AUC_{∞} , following at steady state, will be summarized using the same descriptive statistics as above. LS means (\pm 90% confidence interval [CI]) for log transformed C_{max} , $AUC_{0.24}$, and AUC_{∞} will be evaluated by a linear mixed effects model with a fixed term for treatment and a random term for subject, fit by estimated generalized least squares with restricted maximum likelihood estimates of random effects. If deemed relevant to test for a treatment difference in T_{max} , a Wilcoxon signed rank test will be used.

The plasma pharmacokinetic parameters of olanzapine from Day 17 will be compared with its pharmacokinetic profiles available in published literature.

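### The steady-state AUC∞ ratio counts drug carried over from earlier doses, so it misstates the exposure change if half-life changes; AUC0-24 should carry the comparison

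*SAP*

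**What the plan says.** SAP 5.2.4 forms combination-to-monotherapy ratios for Cmax, AUC0-24 and AUC∞ that "at steady state will be summarized using the same descriptive statistics as above". It then fits log Cmax, log AUC0-24 and log AUC∞ in a mixed model with treatment fixed and subject random. Protocol 8.4 and the synopsis give the same three ratios, "following at steady state, will be summarized using the same descriptive statistics as above".

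Neither document names the days. The sampling plan in SAP 5.2.1 leaves only Day 7 (seventh daily dose, roluperidone alone) and Day 17 (tenth combined dose) as full steady-state profiles. Day 7 sampling ends at 24 h ("16, 18, and 24 hours post-dose on Days 1 and 7"). Day 17 sampling runs to 48 h ("16, 18, 24, 28, 32, 36, and 48 hours post-dose"). Pre-dose samples are also planned "at pre-dose and 6 hours post-dose on Days 3-6" and, in Treatment Phase 2, at "time 0 (pre-dose) and 6 hours post-dose on Days 9-16". The schedule in SAP 1.2 notes that the phases are not separated by a washout.

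SAP Table 1 (5.2.3) defines AUC∞ as AUClast + Clast/λz. It neither restricts this to the single dose nor corrects for carry-over. AUC∞ is reported if half-life can be calculated and Clast/λz "represented 30% or less of the AUC value". Values with a share "less than 30% but greater than or equal to 20% of the AUC value will be flagged in the report".

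**The concern.** Extrapolation to infinity recovers one dose's exposure only when the profile starts with no drug in the body. On Days 7 and 17 the subject already carries drug from earlier doses, so the area after 24 h is not exposure owed to that day's dose alone. The size of that extra area depends on half-life, which an interaction study must allow to change. The AUC∞ ratio then mixes a change in exposure with a change in accumulation.

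SAP 5.2 names the log-transformed AUCs as of interest without ranking them, and the sample-size text in SAP 3.1 says only AUC. If the AUC0-24 and AUC∞ ratios disagreed, nothing in the plan says which one is the interaction estimate. Protocol 1.3 intends the result to guide prescribers.

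**Working it through.** **The plan's own figure.** SAP 3.1 states a maximum imprecision of 20.5% or 30.8% for within-subject SD 0.25 or 0.40. With 12 completers, a paired 90% interval on the log scale and a 90% upper bound on the estimated SD (this assurance level is inferred, not stated), the lower-limit imprecision is 1 − exp(−t(0.95; 11) × SD × √(2/12) × √(χ²(0.90; 11)/11)). That gives 20.52% and 30.75%, so the figures are reproduced. They describe random error and do not cover the distortion below.

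**Inputs from the documents.** Once-daily 64 mg; 7 doses alone, then 10 with olanzapine; no washout; nominal sampling times; AUC∞ = AUClast + Clast/λz.

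**Assumptions.** The documents give no half-life, absorption rate or expected interaction. I take linear one-compartment kinetics, fast absorption, a monotherapy half-life of 6, 9 or 12 h, and an effect on clearance (CL). Let r be the true exposure ratio.

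**Algebra.** For linear kinetics, steady-state AUC0-24 = F × Dose/CL, where F is bioavailability. The area after 24 h is the drug in the body at trough divided by CL. So AUC∞ from a steady-state day = (F × Dose + trough load)/CL. With one compartment and fast absorption this is AUC0-24/(1 − exp(−24λ)), where λ = ln 2/half-life. If clearance alone changes, λ becomes λ/r and

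AUC∞ ratio = r × (1 − exp(−24λ))/(1 − exp(−24λ/r)).

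Example, r = 2 at 12 h: 2 × (1 − 0.25)/(1 − 0.50) = 3.00.

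| True r | 6 h | 9 h | 12 h |
|---|---|---|---|
| 2.0 | 2.50 | 2.79 | 3.00 |
| 1.25 | 1.315 | 1.364 | 1.399 |
| 1.1 | 1.12 | 1.14 | 1.15 |
| 0.8 | 0.77 | 0.75 | 0.73 |

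**Simulation.** Planned doses and nominal times, absorption 2/h, linear-up/log-down trapezoid. The SAP gives no λz window; using the last 3 or last 4 points gave the same results to three decimals.

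| True r | Measure | 6 h | 9 h | 12 h |
|---|---|---|---|---|
| 2.0 | AUC∞ | 2.54 | 2.82 | 3.01 |
| 2.0 | AUC0-24 | 2.02 | 2.01 | 2.01 |
| 2.0 | Cmax | 1.37 | 1.49 | 1.57 |
| 1.25 | AUC∞ | 1.32 | 1.37 | 1.40 |
| 1.25 | AUC0-24 | 1.26 | 1.25 | 1.25 |
| 1.25 | Cmax | 1.09 | 1.12 | 1.14 |

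Cmax is valid for the peak but does not estimate r. With no interaction, or a change in bioavailability only, all three ratios were recovered exactly. At r = 2, AUC∞ reads 2.54, 2.81 and 3.00 with absorption 0.7/h, and 2.55, 2.79 and 2.96 with 0.3/h. A separate run at 0.7/h doubled the volume of distribution with clearance unchanged (half-life 8 to 16 h). Exposure per dose did not change, AUC0-24 read 1.00, and AUC∞ read 1.37.

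**The 30% rule.** The extrapolated share is exp(−λT), with T = 24 h on Day 7 and 48 h on Day 17. With clearance halved, the simulated Day 7/Day 17 shares are 6.7/6.4%, 16.4/16.0% and 25.7/25.2% at 6, 9 and 12 h. At 9 h neither day is flagged, although the ratio is 2.82 against a true 2.0, about 40% too high. At 12 h both days are flagged but kept. The rule tests extrapolation, not carry-over. It is also uneven: the share reaches 30% at a half-life of 13.8 h on Day 7 and 27.6 h on Day 17. An unchanged 14 h half-life gives 30.5% versus 9.3%, so Day 7 is dropped and Day 17 kept.

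**When AUC0-24 is safe.** The fraction of steady state reached on Day 7 is 1 − exp(−168λ): 99.2% at 24 h and 91.2% at 48 h. At 24 h the AUC0-24 ratio reads 1.008, 1.260 and 1.983 for true 1, 1.25 and 2. At 48 h it reads 1.095, 1.348 and 1.971, so the steady-state check matters.

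**The case against.** The strongest reply is that the problem is conditional and largely covered. The documents predict no change in half-life, and their non-exhaustive list of CYP2D6 inhibitors (protocol Attachment 1) does not name olanzapine. At r = 1.1 the AUC∞ error is 2–5%, and at 1.25 it is about 5–12%, below the stated 20.5–30.8% imprecision. AUC0-24 is already in the same model, half-life is a listed parameter, profiles are plotted, and no decision rule uses AUC∞. This limits the importance and stands. It does not make the ratio correct, and a systematic error does not show in the width of an interval.

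Second, the 30%-rule details depend on absorption. At 9 h with clearance halved, absorption at 0.3/h or a 4 h lag raises the Day 7 share to 20.6% or 21.1%, which is flagged. At 12 h a 4 h lag gives 30.4%, and the rule removes Day 7. With very slow absorption (0.1/h) and no interaction, AUC∞ reads 0.94, 0.90 and 0.87, and at r = 1.25 the overstatement vanishes or reverses (1.25, 1.23, 1.21). These results stand, so the flag statements and the 13.8–27.6 h window hold for fast absorption only. They are further ways for the AUC∞ ratio to miss the exposure ratio, not a defence of it.

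Third, relabelling would do less violence to the protocol than deletion. That is a workable minimum. Dropping the term is cleaner, because a modelled ratio with an interval will be read as an interaction estimate.

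**Conclusion.** The concern holds. For linear kinetics, AUC∞ from a steady-state day includes carried-over drug, and its ratio departs from the exposure ratio whenever trough load relative to dose changes. Under the stated assumptions, with clearance as the affected parameter, it overstates a rise and exaggerates a fall. Only the size rests on the one-compartment, fast-absorption and 6–12 h half-life assumptions: roughly 5–12% too high at a true 1.25, and 25–50% too high at a true 2.0.

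The AUC0-24 ratio avoids the error provided both days are near steady state, which holds to about 1% for half-lives up to 24 h. The change should be made, but the trial's primary conclusions do not depend on it.

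**What to change.** In SAP 5.2.4:

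- State that the steady-state exposure ratio is AUC0-24, Day 17 versus Day 7, and that Cmax is kept as the on-treatment peak ratio.
- Remove AUC∞ from the steady-state ratio and the mixed model. Report it descriptively for the Day 1 single dose where the extrapolation rule is met. Day 1 also stops at 24 h, so a long half-life would leave few values.
- State that the planned pre-dose samples (Days 3–7 and 9–17) will be used to check that both days are near steady state, with a criterion for that check, and say whether the same wording covers BFB-520.

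Record the change in SAP Section 7, which now anticipates no deviations. Protocol section 8 allows departures from the protocol analysis to be set out in the SAP before database lock. Align protocol 8.4 and the synopsis at the next formal amendment, which protocol 13.1 requires for any protocol text.

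The cost is a few sentences and one Section 7 entry in a revised SAP before lock, with no new samples or data. The downside is the loss of one redundant comparison and a documented departure from protocol 8.4 until the amendment.
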